APPENDIX 1: PROHIBITED AND RESTRICTED CONCOMITANT MEDICATIONS

The following is an outline of the restrictions on concomitant medications. Any questions regarding prohibited and restricted concomitant medications should be discussed with the [REDACTED] Medical Monitor.

1. Antipsychotics are prohibited during the first month of the study, including clozapine, quetiapine, risperidone, olanzapine, ziprasidone. Addition of any antipsychotic after the first month of the study must be discussed with the Medical Monitor.
2. The following medications are prohibited and must have been discontinued no less than 30 days prior to Study Day 1: mianserin, mirtazepine, nefazodone, cyproheptadine, fluvoxamine, other investigational agents.
3. Centrally-acting anticholinergic medications are prohibited and must have been discontinued no less than 2 weeks prior to Study Day 1. These include, and are not limited to, benzotropine, biperiden, and trihexylphenidyl. Anticholinergic agents that act predominantly on the peripheral nervous system such as tolteradine or oxybutynin, are allowed.
4. Use of acetylcholinesterase inhibitors is allowed.
5. Medications that can prolong QT interval are prohibited. These include, and are not limited to the following:-
 - Antiarrhythmic drugs including quinidine, procainamide, disopyramide, ajmaline, encainide, flecainide, propafenone, amiodarone, sotalol, *d*-sotalol, bretylium, ibutilide, dofetilide, amakalant, semantilide
 - Anticonvulsants including felbamate, fosphenytoin
 - Antidepressants including amitriptyline, nortriptyline, imipramine, desipramine, clomipramine, maprotiline, doxepin
 - Antihistamines including diphenhydramine
 - Antimicrobial and antimalarial drugs including erythromycin, clarithromycin, ketoconazole, pentamidine, quinine, chloroquine, halofantrine
 - Antipsychotics including thioridazine, chlorpromazine, haloperidol, pimozide, ziprasidone, mesoridazine
 - Others including methadone, cocaine
6. Use of amantadine, which may cause QT prolongation, should be discussed with the medical monitor.

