### **5.9.2 Prior, Post and Concomitant Medications**

Medications started prior to the day of the first dose of open-label study medication and continued into the study, or medications started on or after the day of the first dose of study medication and before or on the day of the last dose of the study medication will be reported as concomitant medications. Medications stopped before the first date of study medication dosing will be considered prior medications. Medications started after

the day of last dose of study medication will be considered post-treatment. Prior, concomitant and post-treatment medications will be listed.

The number and percentage of subjects using concomitant medications in each WHO Drug Anatomical/Therapeutic/Chemical (ATC) Level 3 (i.e., pharmacological subgroup) category and preferred term will be summarized. Separate summaries will be presented for

- Anti-psychotic medications
- Medications indicated for dementia
- Medications indicated for motor function
- Medications not included in the preceding 3 categories.

Number of concomitant medications will be summarized at first dose date and last dose date for overall, indicated for motor functions, dementia and antipsychotics.

Antipsychotics taken post-treatment (medication started after the last dose date) will also be summarized. Multiple medications for the same subject may be classified to the same ATC level or preferred name. However, subjects will only be counted once for each level of classification.

Prior, concomitant, and post-treatment medications with the verbatim, ATC level 3 category, preferred term, indication, dosage, route, unit, frequency, and start/stop dates of administration will be provided in a listing.

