- (1) AEs grouped by time period at AE onset: For all TEAEs, serious TEAEs, TEAEs leading to discontinuation of study drug, and TEAEs of special interest (those that may be expected on the basis of pimavanserin's pharmacology, those of special regulatory interest [suicidality, abuse liability etc], and those commonly associated with current antipsychotics), the count and percentage of subjects will be summarized by time period defined in [Section 5.4.2 Table 2](#). The denominator for a time period will be the number of subjects on treatment

(including a 30-day follow-up) during that particular time period. TEAEs with fatal outcome will be summarized by time period at death.

- (2) AEs by age group at AE onset: For all TEAEs, serious TEAEs, TEAEs leading to discontinuation of treatment, and TEAEs of special interest, the count and percentage of subjects will be summarized by age category at the time of AE onset. Age at onset will be categorized as follows:  $\leq 50$  years, 51 - 60 years, 61 – 70 years, 71 – 80 years and 81 - 90 years. The denominator for an age group will be the number of subjects on treatment (including a 30-day follow-up) while in that particular age group. TEAEs with fatal outcome will be summarized by age group at death.

An AE listing by subject will display all events and will include the verbatim term in addition to the MedDRA SOC and preferred term. This listing will also include all relevant CRF data associated with the event: date of onset, date of last dose, severity, outcome, relationship to study drug, action taken, and seriousness.

In addition, AE tables also will be summarized by age group and onset time period for subject with concomitant antipsychotic use and without antipsychotic use.

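### The AE split by antipsychotic use is not tied to AE onset; on the most direct reading, AEs before the first antipsychotic count as with use

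*SAP*

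**What the plan says.** SAP 5.13.1 has one sentence on this split: "AE tables also will be summarized by age group and onset time period for subject with concomitant antipsychotic use and without antipsychotic use". It does not say whether use must come before, on or in the same period as the AE.

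The only definition of concomitant use is in SAP 5.9.2. It covers "Medications started prior to the day of the first dose of open-label study medication and continued into the study" and "medications started on or after the day of the first dose of study medication and before or on the day of the last dose" of study drug. Later starts form a separate class: "Antipsychotics taken post-treatment (medication started after the last dose date) will also be summarized". The same section foresees that some subjects may be on an antipsychotic at entry: "Number of concomitant medications will be summarized at first dose date and last dose date for overall, indicated for motor functions, dementia and antipsychotics".

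Protocol Appendix 1, item 1 states: "Antipsychotics are prohibited during the first month of the study". It also foresees later starts: "Addition of any antipsychotic after the first month of the study must be discussed with the Medical Monitor".

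For age, which also changes during follow-up, SAP 5.13.1 does give a rule tied to onset: "the count and percentage of subjects will be summarized by age category at the time of AE onset". The denominator there is the subjects on treatment while in that age group.

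**The concern.** Antipsychotic use changes over time, but the sentence treats it as a fixed property of the subject. With the SAP 5.9.2 definition, one course at any time on study makes the subject a user in every period and age group. A subject who first takes an antipsychotic in year 3 would bring all AEs since Day 1 into the with column. AEs after the antipsychotic was stopped would count there too.

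This is the only planned view of AEs with and without a concomitant antipsychotic. A reader will use it to ask whether adding an antipsychotic changes risk. If the columns can differ with no true effect, the table cannot answer, and nothing in it would warn the reader.

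**Working it through.** The documents give no figure on this point, so there is none to reproduce. Step 1 uses the documents alone. Steps 2 to 4 are illustrations on assumed rates.

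**1. Days 1–28, no assumed rate.** The first period in SAP Table 2 is Days 1–28, and Protocol 3.1 puts Month 1 at Day 28. A compliant subject who starts an antipsychotic on study therefore starts after this period. Under ever/never, every Days 1–28 AE of such a subject is shown as with use although it came before the antipsychotic. None of these subjects can die in that period. The argument does not cover subjects already on an antipsychotic at entry.

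**2. How much with-column time precedes the antipsychotic.** Assumed: deaths 6 per 100 patient-years; discontinuation 50% per year; antipsychotic start 20% per year from Day 29; constant hazards; no antipsychotic stopping; follow-up to Day 1461.

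- Exit hazard: 0.06 − ln 0.5 = 0.753 per year. Start hazard: −ln 0.8 = 0.223 per year.
- Still on study at Day 29: exp(−0.753 × 28/365) = 0.944.
- Start before exit, given that: (0.223/0.976) × [1 − exp(−0.976 × 1432/365)] = 0.224.
- New starters: 0.944 × 0.224 = 0.211 of subjects not on an antipsychotic at entry.
- Share of the with group that is new starters: with 10% users at entry, 0.9 × 0.211 / (0.9 × 0.211 + 0.10) = 66%; with 30%, 0.7 × 0.211 / (0.7 × 0.211 + 0.30) = 33%; with none, 100%.

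These are also, to rounding, the shares of Days 1–28 with-column time that precede the antipsychotic. By simulation with no users at entry, the share is still 92% in Days 29–91 and about 57% in Days 184–365.

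**3. Treatment-ending AEs, Days 184–365, no true effect.** Two mechanisms oppose each other. A user must stay on study drug until the start, which moves treatment-ending AEs out of the with column (immortal time). An AE that prompts an antipsychotic is moved in. Simulated with 2,000,000 subjects per case and no users at entry; 35% of discontinuations are for AEs, with onset 14 days before last dose; a prompted antipsychotic starts 4 days after onset. The true ratio is 1.

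| With/without ratio, AE discontinuations | Starts unrelated to AEs | 20% of these AEs prompt a start | 40% prompt a start |
|---|---|---|---|
| Ever/never, percentages of subjects | 0.43 | 0.95 | 1.6 |
| Status at onset, percentages with time-updated denominators | 0.86 | 0.77 | 0.69 |
| Status at onset, events per person-time | 0.99 | 0.98 | 0.97 |

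Row 1 can fall on either side of 1. Row 2 stays biased because exposed and unexposed time within a period differ in length. Only row 3 returns about 1.

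**4. Deaths, if they are in the split.** With unrelated starts and no users at entry, the ever/never death ratio in Days 184–365 is about 0.41. Varying the start rate (10–40% per year), deaths (3–12 per 100 patient-years), discontinuation (30–70% per year) and entry use (0–30%) gives 0.25 to 0.92. If use during the period is meant instead, 0.41 becomes about 0.81: less bias, but not none.

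Now suppose an antipsychotic is started 10 days before 20% of on-treatment deaths. Ever/never gives 1.05 to 1.09. Status at death gives 13.3 against 4.9 per 100 patient-years, a ratio of 13.3/4.9 = 2.7. At 40%, ever/never gives 2.0 to 2.2 and status at death 21.2/3.6 = 5.9. For deaths, the onset-based rate can move further from the truth.

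**The case against.** The strongest reply is that ever/never is an inference. SAP 5.9.2 sorts medications into prior, concomitant and post-treatment; it does not say how subjects enter AE columns. SAP 5.13.1 tabulates by onset period with period-specific denominators, which also fits use during the period. This stands: a reader might infer that the SAP prescribes ever/never, and it does not say so. But the narrower reading is written nowhere, and two programmers could build different tables from the sentence. Nor does that reading remove the problem. It reduces immortal time, but an AE that prompts a start in the same period still falls in the with column.

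The sizes rest on assumed rates, and this also stands. At the 400 subjects of Protocol 3.4, the base case puts only about 0.9 deaths in the with cell for Days 184–365.

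A reader might also infer that the split distorts the mortality results. The documents do not support this. SAP 5.13.1 tabulates fatal TEAEs by period or age group at death, while the split sentence speaks of onset period. SAP 5.13.2 mentions no antipsychotic split, and the Kaplan-Meier survival subgroups are age, gender and geographic area.

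Finally, no formal tests are planned, and AE onset dates and medication start and stop dates are listed by subject, so timing can be checked case by case. This limits the severity but does not repair the table.

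**Conclusion.** The point holds, at minor severity. SAP 5.13.1 gives no timing rule for antipsychotic use, and its most direct reading with SAP 5.9.2 counts AEs before the first antipsychotic as with use. For compliant on-study starters this is certain under that reading in Days 1–28, given the current text of Appendix 1. In later periods a gap can arise with no true effect.

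It is tempting to conclude that the table will make antipsychotics look safer. That does not follow: the illustrated ratio for AE discontinuations runs from 0.43 to 1.6 depending on how often AEs prompt a start, and the documents give neither that share nor any antipsychotic rate. The figures show that either direction is possible; they do not predict this trial. The primary objective and the Kaplan-Meier analyses are unaffected.

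**What to change.** In SAP 5.13.1:

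1. Classify each non-fatal TEAE by antipsychotic status on its onset date, using the collected start and stop dates. Put events and person-time before the start in the without column. Treat users at first dose as exposed from Day 1. State how time after an antipsychotic stops, and the 30 days after last dose, are assigned.
2. Make events per 100 patient-years, with person-time split by antipsychotic status, the main comparison. Show percentages as secondary, with a note that they stay biased even with time-updated denominators.
3. State whether fatal TEAEs are in the split. If they are, do not present onset-based death rates as a correction. List deaths with the antipsychotic start date and the interval to death.
4. Flag antipsychotic records whose start date was imputed to Day 1 under SAP 5.4.3, since they would count as exposed from entry.
5. Footnote that Days 1–28 has little exposed time and that confounding by indication remains.

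The cost is SAP wording and programming; the dates are already collected. A subject can appear in both columns, so the column counts will not add up to the safety set.

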### **5.13.2 Deaths and Other Serious and Significant Adverse Events**

Treatment-emergent SAEs, TEAEs leading to discontinuation from the study or study drug, and TEAEs with fatal outcome will be summarized by time period as given in [Table 2](#) in frequency tables by SOC and preferred term. In addition, the overall AE summary table will also be presented for all events (i.e. treatment-emergent plus non-treatment-emergent events).

Subject listings of SAEs, deaths, and AEs leading to discontinuation of study drug will be provided. These listings will provide all relevant eCRF data for each event including the date/study day of onset, date/study day resolved, date of last dose/study day of last dose, severity, outcome, relationship to study drug, action taken, and seriousness.

Kaplan-Meier estimates of percent surviving subjects at 6 months, 1 year, 1.5 years, 2 years, 2.5 years, 3 years, 3.5 years and 4 years, as well as median survival time will be computed for all subjects and by subgroups: baseline age group ( $\leq 75$  years old or  $>75$  years old), gender (female or male), and geographic area (North America or outside North America). If a subject is deceased, the survival time will be calculated as death date minus first dose date + 1; otherwise the survival time will be censored at the last dose date (for subjects who have discontinued from the study) or database snapshot date (for ongoing subjects).

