4.2 Criteria for Subject Withdrawal

In accordance with the Declaration of Helsinki and other applicable regulations, a subject has the right to withdraw from the study at any time and for any reason without prejudice to his or her future medical care.

Subjects may be discontinued or withdrawn from the study for a number of reasons, including but not limited to those listed below:

- Adverse events(s) (serious or non-serious)
- Disease progression
- Subject's voluntary withdrawal of consent
- The Investigator determines that continuation in the study would be detrimental to a subject's well-being because of development of a serious illness, any other significant change in clinical status, or any other compelling medical reason
- Subject fails to comply with protocol requirements
- At discretion of Sponsor
- Lost to follow-up
- Death
- Female subject becomes pregnant

If a subject withdraws or is terminated from the study, all efforts must be made to complete the procedures for End-of-Study (see [Table 1](#)). Furthermore, a reason for withdrawal from the study must be provided on the appropriate page of the electronic CRF (eCRF) and in the subject's medical record. If the subject terminated due to an AE, this event must be reported in accordance with procedures described in [Section 6.2.7](#) (Adverse Events) of this protocol. Additional visits may be scheduled as medically indicated.

If a subject is withdrawn due to an AE, the Investigator will arrange for a follow-up visit with the subject, as appropriate, until the event has resolved or stabilized. Efforts must be made to follow the course of the AE and to document its progress and resolution as described in [Section 6.2.7](#) in this protocol.

For subjects who withdraw consent, further information for inclusion in the clinical trial database will not be collected, with the exception of information regarding ongoing AEs at the time of withdrawal.

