6.2.7. Adverse Events

Adverse events will be recorded for all subjects during the Week 2 visit, Month 1 visit, Month 3 visit, Month 6 visit, Month 9 visit, Month 12 visit and every 6 month visit thereafter, and if a subject withdraws or is terminated from the study, at an End-of-Study visit.

Occurrence of AEs after the informed consent is signed and prior to the first administration of investigational drug in this study will be recorded as part of the Updated Medical History taken on Day 1 (Baseline). Once the first dose of investigational drug is taken on Day 1 any subsequent AEs are to be recorded on the CRF page for AEs.

All AEs must be followed until resolution, until the condition stabilizes, until the event is otherwise explained or is judged by the investigator to be no longer clinically significant, or until the subject is lost to follow-up. The investigator is responsible for ensuring that follow-up includes any supplemental investigations necessary to elucidate as completely as practical the nature and/or causality of the AE. This may include additionally laboratory tests or investigations histopathological examinations or consultation with other health care professionals.

Investigators are not obliged to actively seek AE information from former study participants. However, if the investigator learns of an SAE at any time after a subject has been discharged from the study and the event may reasonably be considered related to the use of the study drug, the investigator should promptly telephone the Medical Monitor.

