For life-threatening or fatal events, the Investigator (or designee) must call the Medical Monitor immediately. All SAEs must be reported within 24 hours of discovery by fax to [REDACTED]. If it is not possible to fax the SAE form within the 24-hour timeframe, the SAE may be reported by telephone. All contact details are provided in the Investigator Site File/Regulatory Binder.

It is the Investigator's responsibility to notify the responsible IRB/EC regarding new and significant safety information, including expedited safety reports. The Investigator will be responsible for forwarding any additional information to the IRB/EC in accordance with specific agreements and/or local requirements.

Subjects in this study will be followed for any SAEs and/or unexpected events by the Investigator until the abnormal parameter or symptom has resolved or stabilized. These events

should continue to be reported within 24 hours of discovery, particularly life-threatening or fatal events, and the Investigator should continue to provide reports to the IRB/EC, as required. In the event of any SAE (other than death), the subject will be instructed to contact the Investigator (or designee) using the telephone number provided in the subject information sheet. All subjects experiencing an SAE will be seen by the Investigator or designee as soon as is feasible following the report of the SAE.

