aforementioned subgroups. For this analysis, if a subject has an AE leading to study termination or drug withdrawal, the time to event will be calculated as last dose date minus first dose date + 1; otherwise the time to event will be censored at either last dose date (for subjects who discontinued due to reasons other than AE) or database snapshot date (for ongoing subjects).

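### The survival curve counts deaths at any time after last dose but drops surviving leavers at last dose

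*SAP*

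**What the plan says.** SAP section 5.13.2 plans Kaplan-Meier survival at half-yearly points from 6 months to 4 years, with median survival, overall and by age group, sex and geographic area. It sets three end dates:

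- **Recorded as dead:** "the survival time will be calculated as death date minus first dose date + 1". No limit after last dose is given.
- **Discontinued, not recorded as dead:** "otherwise the survival time will be censored at the last dose date (for subjects who have discontinued from the study").
- **Ongoing:** censored at the database snapshot.

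Elsewhere the SAP uses matched windows. In section 5.7.1, the Kaplan-Meier analysis of AEs leading to termination places the event at last dose, and "otherwise the time to event will be censored at either last dose date (for subjects who discontinued due to reasons other than AE"). Time on treatment also ends at last dose for subjects who stop. In section 5.13.1, the AE denominators count subjects on treatment, "including a 30-day follow-up) during that particular time period". That 30-day tail is not carried into the survival rule, and SAP section 6 does not mention the point.

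The Protocol governs which deaths after last dose can be recorded:

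- Section 6.2.7.2: subjects "will be followed for any SAEs and/or unexpected events by the Investigator until the abnormal parameter or symptom has resolved or stabilized".
- Section 6.2.7: a report is expected "if the investigator learns of an SAE at any time after a subject has been discharged from the study" and the event may be drug-related, but "Investigators are not obliged to actively seek AE information from former study participants".
- Section 4.2: after consent withdrawal, "further information for inclusion in the clinical trial database will not be collected", except for AEs ongoing at that time.

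**The concern.** A Kaplan-Meier risk set must be fixed by what is known at each time, not by what happens later. Here, whether a discontinued subject counts as at risk after last dose depends on whether that subject is later recorded as dead. Those who die carry their post-dose time into the curve. Those who survive carry none, even when they were seen alive, for example at an End-of-Study visit, where Protocol Table 1 schedules no study drug.

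The study's objective is long-term safety, and this is the SAP's only survival curve. The pull grows with follow-up, because each late death falls on a risk set reduced to subjects still on drug plus those who will die. It can also differ between subgroups if stopping or late reporting differs. A reader of the curve could not say how much of a late fall comes from the censoring rule.

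**Working it through.** The documents state no survival, death or discontinuation figure, so there is nothing of the plan's own to reproduce. The check has three steps.

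**1. Direction.** The estimator is S(t) = product over death times of (1 − d/n), where d is deaths and n is the number at risk. Hold the recorded deaths fixed and compare the SAP rule with one that keeps leavers who survive at risk over the same post-dose window. Every d is unchanged. Under the SAP rule every n is equal or smaller, because those survivors have already been removed. Each factor, and so the curve, is equal or lower.

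**2. Worked example.** Of 100 subjects, 20 stop on day 100, two of those 20 die on day 130, and 80 are ongoing to day 400.

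- SAP rule: at day 130, n = 80 + 2 = 82, so S = 1 − 2/82 = 97.56%.
- Matched 30-day tail: n = 80 + 20 = 100, so S = 1 − 2/100 = 98.00%.
- Both cut at last dose: no events, S = 100%.

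The same two deaths weigh 100/82 = 1.22 times as much under the SAP rule.

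**3. Size under stated assumptions.** None of these rates is in the documents except N:

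- death rate 6 per 100 person-years on drug, 30 per 100 in the first 30 days after stopping, then 6 per 100;
- exponential stopping at 0.4 or 0.7 per year;
- snapshot uniform between 0.5 and 4.5 years after first dose;
- all deaths within 30 days of last dose recorded, and a share of leavers (0%, 5% or 10%, independent of outcome) also tracked beyond day 30;
- N = 400 for sampling error (Protocol section 3.4 anticipates at least 400).

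The matched rule counts the same deaths. It keeps tracked leavers at risk to the snapshot and other leavers to last dose plus 30 days. The figures are large-sample limits, confirmed by simulating 2,000,000 subjects per scenario. Estimated mortality:

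| Stopping rate | Tracked beyond day 30 | Time | SAP rule | Matched, same deaths |
|---|---|---|---|---|
| 0.7/yr | 0% | 2 years | 14.3% | 13.6% |
| 0.7/yr | 0% | 4 years | 26.6% | 25.4% |
| 0.7/yr | 5% | 2 years | 14.8% | 13.5% |
| 0.7/yr | 5% | 3 years | 22.2% | 19.4% |
| 0.7/yr | 10% | 2 years | 15.3% | 13.4% |
| 0.7/yr | 10% | 3 years | 23.6% | 19.2% |
| 0.4/yr | 0% | 2 years | 13.0% | 12.6% |
| 0.4/yr | 0% | 4 years | 24.4% | 23.7% |
| 0.4/yr | 10% | 2 years | 13.5% | 12.6% |
| 0.4/yr | 10% | 3 years | 20.1% | 18.2% |

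At 0.7 per year, 10% tracking means about 3 late deaths per 400 subjects. Dropping those deaths and cutting both events and censoring at last dose plus 30 days gives 13.6% and 19.7% at 2 and 3 years, close to the matched 13.4% and 19.2%. The excess therefore comes from the uneven censoring, not from whether late deaths are counted.

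A separate simulation used equal hazards on and off drug (0.05 to 0.10 per year) and stopping at 0.3 to 0.6 per year. The SAP rule understated 4-year survival by about 0.3 to 1.6 points if all deaths to 30 days were recorded, and by 1.1 to 4.2 points to 90 days. Complete recording to 365 days gave 5 to 17 points, which the Protocol's passive reporting makes an extreme case. Matched rules came within about 1 point of the true value.

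**Against true mortality.** If the rate of 30 per 100 person-years persists after stopping and deaths beyond day 30 go unrecorded, the SAP rule gives 14.3% at 2 years against a true 27.9% (stopping 0.7 per year). The direction then reverses.

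**The case against.** The strongest objection concerns size. No document supports 5% or 10% tracking. Reporting after discharge is passive and limited to possibly drug-related SAEs, and collection largely stops after consent withdrawal. Without late recording, the 2-year gap of 0.4 to 0.7 points is well below the sampling SD of about 2.9 points (N = 400, stopping 0.7 per year). The 4.4-point gap at 3 years is also below one SD, which is about 5.0 to 5.5 points there. This stands as a limit on size. It does not make the rule valid: the error is systematic, does not shrink with more subjects, and the SAP sets no limit that would keep it small.

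Other points stand in part:

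- Death listings show the last dose date, so post-dose deaths can be found from planned outputs. Their effect on the curve still needs a rerun.
- Last dose is the natural event date in the section 5.7.1 analyses, so they show a workable matched rule rather than a breached convention.
- The analysis is single-arm and descriptive, and lower survival may look cautious. The reversal above shows that caution is not assured.
- A last dose plus 30 days rule credits leavers with up to 30 days that may not have been observed, and drops later deaths even when they follow an on-treatment SAE. In the reversal scenario it gives 13.6%, further from 27.9% than the SAP rule. No censoring rule can recover deaths that were never recorded.

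**Conclusion.** The concern holds. For discontinued subjects, section 5.13.2 uses one end date for recorded deaths and another for everyone else, and nothing elsewhere in the SAP or Protocol restores a common window. Relative to a matched rule on the same deaths, estimated survival is equal or lower.

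The size depends on how many late deaths reach the database. Under the assumptions above it is about 1 point or less if recording stops at 30 days, and several points by year 3 if about 3 late deaths per 400 subjects are added. Ongoing subjects are handled correctly. The asymmetry is certain from the text; its size in this trial is not. It should be corrected because the curve bears on the main objective and the change is small, but it does not undermine the rest of the safety analysis.

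**What to change.** Replace the survival rule in SAP section 5.13.2 with one window for events and censoring:

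- Count a death as an event only if it falls on or before the earlier of last dose plus 30 days and the snapshot.
- Censor every other discontinued subject, including those who die later, at that same date.
- Censor ongoing subjects at the snapshot.
- Do not cut survivors back to an earlier last contact while still counting deaths to day 30; that brings the asymmetry back.

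State the assumption that deaths within 30 days of last dose are reported. Because no visit is scheduled 30 days after last dose, add an on-treatment curve as a check, with both deaths and censoring ending at last dose. List deaths beyond 30 days. Show a curve of all known deaths only if a last-known-alive date can be derived from data already collected.

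Thirty days matches the follow-up in the SAP's AE denominators. The curve will still not equal the fatal-TEAE tables, because treatment-emergent status depends on AE onset.

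The cost is one SAP sentence and one derived variable, built from last dose, death and snapshot dates the SAP already uses, plus the added check curve. The downside is that deaths beyond 30 days leave the main curve, and the result rests on complete reporting within 30 days.
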